7.3.4 Interim analyses

Analysis of baseline characteristics will be performed during the conduct of Phase II and Phase III on a regular basis in order to assess comparability of VKA and dabigatran treatment cohorts and potential other treatment groups. The comparability of the patient baseline characteristics prescribed either VKAs or dabigatran will be evaluated at regular intervals (e.g. approximately twice per year, dependent on the recruitment). For these analyses appropriate statistical methods, which will include propensity scores will be used to assess channeling bias. The decision to start with Phase III will be made by the steering committee (SC) and will be based on the interim analyses performed in context of the global study Phase II and III (1160.129, [U11-1638-03](#)),

Additional types of interim analyses will be performed in context of the global study (1160.129), including regional analyses of Phase II / Phase III baseline data.

At the time of those analyses or afterwards, additional interim analyses on the baseline and/or follow-up data for the EU/EEA patients (i.e. all patients included in 1160.136 study) might be done (including e.g. respective analysis on compliance with SmPC).

7.4 HANDLING OF MISSING DATA

In order to assess the effects of lost to follow-up patients, percentages of dropouts and reason for loss to follow-up will be summarized in patients with a pre-planned follow up (such as patients initiating dabigatran in Phase II and all patients in Phase III). In addition baseline characteristics of patients who were lost to follow-up in comparison to patients with a complete follow-up will be described.

Any reasonable attempt will be undertaken to ensure completeness of data collection in this registry. Imputation might be performed dependent on amount and distribution of missing values.

7.5 RANDOMISATION

Not applicable.

7.6 DETERMINATION OF SAMPLE SIZE

It is planned to recruit approximately 5,000 patients in Phase II and approximately 10,000 patients in Phase III.

The number of patients included in Phase II and duration of enrollment is not driven by a formal sample size calculation but is primarily dependent on the availability of eligible patients treated with dabigatran and on the presence of channeling bias.

Throughout the Registry Program the aim is to describe characteristics of the newly diagnosed non-valvular AF population in treatment regimen cohorts and overall by calculation of estimates and confidence intervals for relevant attributes. The following paragraphs describe the statistical precision (width of 95% confidence interval) when estimating prevalence and incidence.

Proprietary confidential information.

© 2014 Boehringer Ingelheim International GmbH or one or more of its affiliated companies. All rights reserved.

This document may not - in full or in part - be passed on, reproduced, published or otherwise used without prior written permission.

Estimates for proportions/prevalences (Phase II-III)

Categorical attributes will be estimated with the following precision (i.e. width of descriptive 95% confidence interval), depending on sample size and prevalence of the attribute:

Table 7.6: 1 Width of 95% confidence interval dependent on attribute prevalence and sample size

| Attributes prevalence [%] | | Sample size (for subgroup or overall) | | | | | |
|---------------------------|--------------|---------------------------------------|------|------|------|------|-------|
| | | 500 | 1000 | 2000 | 4000 | 5000 | 10000 |
| 5 | Expected n | 25 | 50 | 100 | 200 | 250 | 500 |
| | 95%-CI width | 4.03 | 2.81 | 1.96 | 1.38 | 1.23 | 0.86 |
| 10 | Expected n | 50 | 100 | 200 | 400 | 500 | 1000 |
| | 95%-CI width | 5.46 | 3.82 | 2.68 | 1.88 | 1.68 | 1.19 |
| 20 | Expected n | 100 | 200 | 400 | 800 | 1000 | 2000 |
| | 95%-CI width | 7.2 | 5.05 | 3.55 | 2.5 | 2.24 | 1.58 |
| 30 | Expected n | 150 | 300 | 600 | 1200 | 1500 | 3000 |
| | 95%-CI width | 8.21 | 5.77 | 4.06 | 2.86 | 2.56 | 1.81 |
| 40 | Expected n | 200 | 400 | 800 | 1600 | 2000 | 4000 |
| | 95%-CI width | 8.77 | 6.17 | 4.34 | 3.06 | 2.74 | 1.93 |
| 50 | Expected n | 250 | 500 | 1000 | 2000 | 2500 | 5000 |
| | 95%-CI width | 8.94 | 6.29 | 4.43 | 3.12 | 2.79 | 1.97 |

For Phase II a total sample size of 5,000 patients allows an estimation of a population attribute with a precision of less than 2.8% (i.e. width of 95% CI).

For subgroups which consist of at least 500 patients; this allows an estimation of a population attribute within the subgroup with a precision of approximately 8.9% (i.e. width of 95% CI).

For Phase III a total sample size of 10,000 patients allows an estimation of a population attribute with a precision of less than 2.0% (i.e. width of 95% CI).

Estimates for incidence rates (Phase II-III):

Estimates and confidence intervals for incidence rates (interpreted on a descriptive level) will be computed. For Phase II it is estimated to recruit approximately 2,500 patients from EU/EEA member states in the dabigatran treatment cohort whom are followed up for up to 2 years. Assuming a total treatment discontinuation and lost to follow-up rate of 25% per year a

Proprietary confidential information.

© 2014 Boehringer Ingelheim International GmbH or one or more of its affiliated companies. All rights reserved.

This document may not - in full or in part - be passed on, reproduced, published or otherwise used without prior written permission.

total of approximately 3,802 patient-years in patients from EU/EEA member states starting dabigatran will be observed.

When observing 3,802 dabigatran patient years, we will observe at least one patient with an event (ADR, MBE, stroke/SEE, etc), if the underlying incidence rate for this event is 0.079 occurrences per 100 patient years or above with a power of 95%. If we do not observe any event within the 3,802 patient years, it can be excluded with 95% confidence that the underlying true event rate is above 0.079 per 100 patient years in the population.

Based on the recent RE-LY trial (warfarin, dabigatran), it is expected that the incidence rates for stroke/SEE and MBE will be in a range of 1 to 3 per 100 patient years in the total population. The width of the two-sided 95% confidence interval of the population depends on the obtained estimate from the sample of 3,802 patient years; the following table illustrates this relationship:

Table 7.6: 2 95% Confidence intervals based on different scenarios for observed event rates (based on 3,802 patient years)

| Observed event rate per 100 patient years | Lower 95% CI for event rate per 100 patient years | Upper 95% CI for event rate per 100 patient years |
|---|---|---|
| 1 | 0.70773 | 1.372465 |
| 2 | 1.575877 | 2.503151 |
| 3 | 2.474761 | 3.603743 |

The calculation of confidence intervals is based on the method described in Hahn, Meeker (section 7.2.2; using χ^2 -quantiles). ([R12-3048](#))

As an example, assume that the event rate for stroke per 100 patient years is 1, i.e. we observe ~38 strokes within the 3,802 patient years. The two-sided 95% confidence interval for the population incidence rate per 100 patient years is 0.71 to 1.37. Thus it can be excluded with 95% confidence that the true rate of strokes per 100 patient years is above 1.37 in the population.

For Phase III, for treatment group cohorts which initially consist of at least 2,000 patients, approximately 4,019 patient-years will be observed within the treatment regimen cohort. This approximation is based on the assumptions of a total treatment discontinuation and lost to follow-up rate of 25% per year and an individual follow-up of three years. Therefore, due to the longer individual follow-up in Phase III and thereby the longer observation time per patient, estimates of incidences based on treatment regimen cohorts which initially consist of 2,000 patients will have approximately the same precision as described above (for 2,500 patients in Phase II).

95% confidence intervals will be calculated for several outcome events. Therefore, it can be expected that false positive significant differences may arise, i.e. a treatment regimen cohort may appear by chance with a lower or a higher incidence rate for specific outcome events or for the composite endpoint variable; consequently, results have to be interpreted with care.

Proprietary confidential information.

© 2014 Boehringer Ingelheim International GmbH or one or more of its affiliated companies. All rights reserved.

This document may not - in full or in part - be passed on, reproduced, published or otherwise used without prior written permission.

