2. If some overlap is achieved, but comparability is expected not to be achievable in Phase II within the following six months due to persistent channeling bias, then Phase III will be started and a matched analysis will be conducted, being aware of the draw back that the power could not be sufficient for all outcomes.
3. If little or no overlap is achieved, and it appears highly unlikely that comparability would be achievable even if the study were extended for a prolonged period of time as significant channeling bias persists, then a separate database study based on existing data (e.g. claims data, electronic medical records) on long-term outcomes will be initiated to ensure sufficient power within matched cohorts.

The variables that will be considered for matching in scenario 2 and 3 will consist of a subset of those that were used for the assessment of comparability. Their choice will be based on the strength of the association of those variables with the outcome under study and the learnings from the interim results. At least age and gender will be matching variables. In addition, scores derived from those variables (e.g. the estimated propensity score) could be considered as a matching variable.

The study described in this protocol will collect data in up to 23 European countries (for planned participating countries see [Appendix 10.3](#)) in up to about 680 sites and is planned to involve as many as 2,000 investigators. It is planned to enroll approximately 5,000 patients in Phase II and another 10,000 patients in Phase III.

The planned registry period is from July 2011 to June 2020, which covers the total expected duration of Phase II and III.

Enrollment into Phase III of the global study will end after the overall enrollment goal has been met, or by June 2017, whichever comes first. Individual regions may end earlier depending on recruitment.

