3.2.1 Potential for bias and confounding

Selection bias

Selection bias may occur on two different levels: The site level and the patient level. If sites where dabigatran is most used differ systematically with respect to patients or routine procedures from sites in which it is less used, the between-site difference would lead to noncomparability between dabigatran patients and others, even if no clinician accounted for patient characteristics in his or her decision to use the product.

To minimize selection bias at the site level, the goal is to have participating centers reflect a (country specific) balance between general practices, specialist offices, community hospitals, university hospitals, outpatient care centers and anticoagulation clinics. Basic characteristics

Proprietary confidential information.

© 2014 Boehringer Ingelheim International GmbH or one or more of its affiliated companies. All rights reserved.

This document may not - in full or in part - be passed on, reproduced, published or otherwise used without prior written permission.

of sites that did not participate will be summarized.

Selection bias at the patient level might occur if for example, sites preferentially reported "interesting" cases to the Registry, and particularly if they did so differently for initiators of dabigatran and VKAs. To minimize selection bias at the patient level, consecutive patients from each site who meet entry criteria of this Registry Program are expected to be invited to participate in the registry.

Consecutive enrollment of patients to avoid selection bias should be emphasized. As participation in another international registry is an exclusion criteria for entry into the study (please refer to section 3.3.3), parallel enrollment in another international registry on the use of oral anticoagulation in AF in the same department should be avoided, as otherwise consecutive enrollment would be challenging. In addition, it should be ensured that both dabigatran and VKAs are available at participating sites or that availability for both treatment options is foreseen in the near future. In the latter case, information on treatment availability has to be documented.

Loss to follow up

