7.3 PLANNED ANALYSES

Analyses will be performed by Boehringer Ingelheim or Boehringer Ingelheim's designees.

A final analysis and a report of Phase II will be prepared once the data collection of Phase II is completed, the data are cleaned and the database is locked. The final analysis of Phase III

Proprietary confidential information.

© 2014 Boehringer Ingelheim International GmbH or one or more of its affiliated companies. All rights reserved.

This document may not - in full or in part - be passed on, reproduced, published or otherwise used without prior written permission.

(if conducted) will be done after Phase III is completed, the data are cleaned and the database is locked. It will be described in a combined report of Phases II and III together.

Analyses on a country level might be performed in addition, once the report or interim report of phase II (or phase III) is available or if required due to regulatory requirements.

The main analysis population will consist of all eligible patients (i.e. all patients fulfilling all inclusion criteria and no exclusion criteria) and the analysis will focus on the antithrombotic treatment choice for stroke prevention at baseline.

Summary statistics for continuous variables will include the N, mean, standard deviation, minimum, Q1 (lower quartile), median, Q2 (upper quartile), and maximum value; tabulations of categorical variables will present all possible categories and will display the number of observations per category as well as percentages. All estimates will be presented with 95% confidence intervals.

Additionally, similar primary and other analyses as described for the total Registry Program also will be conducted using data from only patients enrolled in the EU/EEA member states covered by this protocol (1160.136).

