6.5 POOLING OF CENTRES

Not applicable.

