For all patients the descriptive summary will include the proportion of patients who completed study, reasons for premature discontinuation of study (including information on availability of vital status information), proportion of patients who permanently stopped antithrombotic treatment selected at baseline (as described in [Table 6.1.2:1](#)), and the reason for permanent stop of medication, if applicable. This analysis will be done per antithrombotic treatment prescribed at baseline using the long-term treatment information.

Summary statistics for continuous variables will include the N, mean, standard deviation, minimum, Q1 (lower quartile), median, Q3 (upper quartile), and maximum value; tabulations of categorical variables will present all possible categories and will display the number of observations per category as well as percentages. The number/percentage of missing values will be present as a separate category.

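### Protocol 7.6 states full-phase confidence interval widths that hold only for independent patients; near 50% prevalence a very small within-site correlation breaks the stated limits

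*Protocol*

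**What the plan says.** On size, Protocol 7.6 states: "It is planned to recruit approximately 5,000 patients in Phase II and approximately 10,000 patients in Phase III". It then describes what these numbers deliver through a table titled "Width of 95% confidence interval dependent on attribute prevalence and sample size". Prevalence and sample size are the only inputs. From the 50% row it draws two limits for the full phases: a width below 2.8% for 5,000 patients, and "For Phase III a total sample size of 10,000 patients allows an estimation of a population attribute with a precision of less than 2.0" per cent. Neither limit is qualified.

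On sites, Protocol 3.1 plans data collection "in up to about 680 sites and is planned to involve as many as 2,000 investigators". Section 3.2.1 asks for consecutive enrolment at each site and a balance of site types, from general practices to university hospitals and anticoagulation clinics.

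On intervals, Protocol 7.3 states: "All estimates will be presented with 95% confidence intervals". SAP section 7, which covers Phase III only, repeats most of the surrounding text on summary statistics: "tabulations of categorical variables will present all possible categories and will display the number of observations per category as well as percentages". It does not repeat the sentence on intervals. SAP 7.6 summarises baseline data descriptively and gives an interval formula for incidence rates only, a plain Poisson one. The text provided contains no ICC, design effect, site random effect or site-clustered variance.

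**The concern.** Patients at one site share prescribers, referral patterns and local practice. If these make patients within a site more alike than patients from different sites, 10,000 patients carry less information about a proportion than 10,000 independent ones. An interval that ignores this is too narrow.

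Two features make it worth raising here. The 50% widths in the table (2.79 and 1.97) lie just under the stated limits (2.8 and 2.0), so there is almost no slack. And the first main objective is the choice of antithrombotic treatment, a decision made by prescribers at sites. For a registry without confirmatory hypotheses, interval width is the only measure of adequacy that 7.6 offers, so it should describe the design actually used.

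**Working it through.** **Inputs.** Sizes 5,000 and 10,000, and limits 2.8 and 2.0 percentage points (Protocol 7.6). Up to about 680 sites (Protocol 3.1). Confidence level 95%, two-sided (Protocol 7.3). The ICC is an assumption shown as a range. I take all 680 sites as active and equal in each phase; Protocol 6.1 invites the selected sites to both phases.

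**Step 1: reproduce the plan's figures.** For n patients and x = n × prevalence, the exact (Clopper-Pearson) limits are the 2.5% quantile of Beta(x, n − x + 1) and the 97.5% quantile of Beta(x + 1, n − x). At 50% prevalence the width is 2.791 for n = 5,000 and 1.970 for n = 10,000. All 36 widths in Table 7.6:1 match to rounding. Wald intervals give 2.772 and 1.960 and do not match the table. The arithmetic is right, and the method assumes independent patients.

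**Step 2: allow for sites.** Patients per site: m = 5,000/680 = 7.35 and 10,000/680 = 14.71. Design effect: DEFF = 1 + (m − 1) × ICC. Clustered width = exact width × √DEFF. For example, Phase III at ICC 0.05: DEFF = 1 + 13.71 × 0.05 = 1.685, and 1.970 × √1.685 = 2.56.

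Widths at 50% prevalence, in percentage points:

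| Assumed ICC | Phase II DEFF | Phase II width | Phase III DEFF | Phase III width |
|---|---|---|---|---|
| 0 (as planned) | 1 | 2.79 | 1 | 1.97 |
| 0.005 | 1.032 | 2.84 | 1.069 | 2.04 |
| 0.01 | 1.064 | 2.88 | 1.137 | 2.10 |
| 0.02 | 1.127 | 2.96 | 1.274 | 2.22 |
| 0.05 | 1.318 | 3.20 | 1.685 | 2.56 |
| 0.10 | 1.635 | 3.57 | 2.371 | 3.03 |

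In Phase III the effective sample size (10,000/DEFF) is about 5,930 at ICC 0.05 and 4,220 at ICC 0.10.

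**Step 3: find where the limits fail.** Break-even ICC = ((limit/width)² − 1)/(m − 1), using the unrounded exact widths.

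| Prevalence | Phase II width | Break-even ICC | Phase III width | Break-even ICC |
|---|---|---|---|---|
| 50% | 2.791 | 0.0010 | 1.970 | 0.0023 |
| 40% | 2.735 | 0.0076 | 1.930 | 0.0054 |
| 30% | 2.560 | 0.031 | 1.806 | 0.0165 |
| 20% | 2.237 | 0.089 | 1.578 | 0.044 |
| 10% | 1.683 | 0.28 | 1.186 | 0.13 |

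At 50% prevalence the between-site standard deviation is √(ICC × 0.25). The break-even values therefore correspond to sites differing with a standard deviation of about 1.6 points (Phase II) and 2.4 points (Phase III).

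**Step 4: vary the site assumption.** With 340 equal sites, or 680 sites whose sizes have a coefficient of variation of 1, ICC 0.01 to 0.05 gives 2.98 to 3.62 in Phase II and 2.23 to 3.06 in Phase III. A subgroup of 500 spread over all sites has 500/680 = 0.74 patients per site, so the 8.9% figure in 7.6 is hardly affected. It would be affected if the subgroup came from few sites.

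**The case against.** The strongest reply is that 7.6 is a planning illustration for descriptive intervals. It states that Phase II size is not driven by a formal calculation, and Protocol 7.2 foresees no confirmatory testing. No decision turns on 1.97 versus 2.2, and at ICC 0.01 the widths grow by only about 3% (Phase II) and 7% (Phase III). That stands, and it limits the consequence to overstated precision. A reader might infer that the sample size itself is invalid; the documents do not support that.

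It is also true that the limits are fragile only near 40–50% prevalence. Phase II does plan for that region, with about 2,500 of 5,000 patients starting dabigatran. In Phase III, treatment choice is split over seven groups (SAP Table 6.1:1), and SAP section 4 reports lower dabigatran uptake than expected, so many shares should be well below 50%. Even so, the tabulated full-phase width at each prevalence is somewhat too narrow for any positive ICC.

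Three further readings are tempting and should not be made:

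- That the protocol expects sites to differ. The clause "the between-site difference would lead to noncomparability between dabigatran patients and others" follows a condition, concerns selection bias, and gives no size of between-site variation.
- That SAP 6.5 dismisses clustering. Its "Not applicable" answers whether centres are pooled and says nothing about variance.
- That the SAP has withdrawn the baseline intervals. It is silent on them. SAP section 3 bases the document on Protocol section 7, and SAP section 4 lists no such change, so the requirement in Protocol 7.3 still stands. The Phase II analyses are in a separate plan, so nothing in this SAP bears on them.

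Finally, clustered variance treats sites as a sample from a wider set, although they are chosen for balance. That is one defensible target, and it does not deal with how sites were selected. It does fit the claim in 7.6 to estimate an attribute of the population.

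**Conclusion.** The point holds in a limited form. The stated limits of 2.8% and 2.0% are correct exact-binomial results for independent patients, but they are given without that condition for patients enrolled within sites. At 50% prevalence, the case that sets the limits, an ICC of about 0.001 (Phase II) or 0.0023 (Phase III) is enough to break them. Over ICC 0.005 to 0.05 the widths are about 2 to 15% larger than stated in Phase II and about 3 to 30% larger in Phase III. At 20–30% prevalence the limits survive moderate correlation.

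This rests on an assumed ICC and on 680 equal, active sites. Because 680 is a ceiling, and real sites will differ in size, the site assumption favours the plan.

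**What to change.** - **Protocol 7.6:** say that Table 7.6:1 assumes independent patients, and restate the two full-phase widths over a declared ICC range. For ICC 0.005 to 0.05 these are about 2.8–3.2% for Phase II and 2.0–2.6% for Phase III at 50% prevalence. The subgroup figure can stay, with a note that it supposes patients spread over many sites.
- **Phase III SAP, sections 7 and 7.6:** state explicitly that treatment-choice proportions and key baseline attributes carry the 95% intervals required by Protocol 7.3, computed with site-clustered (robust) variance.

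The cost is a slightly less favourable stated precision, some SAP wording and minor programming with a survey-type procedure. No additional patients or data are needed, since patient data and site characteristics are already entered by site in the electronic system (Protocol 6.1 and 8.3).
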